7.1 Subjects Disposition

The subject disposition summary will include the number screened, the number of screen failures, the number enrolled, the number in each patient population for analysis, the number who completed the study, the number who discontinued the study and reason for discontinuation from the study. Disposition data will be summarized by treatment and overall.

A by-subject data listing of study completion information including the reason for study discontinuation will be presented. A by-subject listing of inclusion/exclusion criteria not met will also be presented.

7.2 Protocol Deviations

A summary of all protocol deviations on ITT population by type will be generated. Protocol deviation data will be summarized by treatment and overall. A by-subject data listing of protocol deviations will also be presented.

All protocol deviations will be presented in a data listing.

7.3 Demographic and Baseline Characteristics

Demographic and baseline characteristic data summarization will be performed to descriptively assess the comparability of treatment groups. Data to be tabulated will include age, race, ethnicity, height, weight, and BMI, as well as baseline characteristics related to medical history, including hypertension, diabetes, smoking history.

7.4 Study Drug Exposure

At Baseline visit, Subjects will receive a kit containing (2) two 30 ml white bottles. Each bottle will be used for 2 weeks. At Week 4, subjects will return the used bottles from the kit and will be issued a new kit of two 30mL white bottles to be used from Week 4 through Week 8.

The cumulative amount of study drug exposure will be estimated by calculating the difference between the weight of the 2 bottles of drug at the time the drug was dispensed at Baseline/Week 4 and the weight of the 2 bottles at Week 4/Week 8. Differences will be summed together.

The amount of product used per day will be estimated by dividing the change by the number of days the subject was on treatment. These weights will be compared to the weight of the product that would be used if the subject was compliant with the protocol. Percent compliance will be calculated as follows:

$$\text{Percent compliance} = \left[\frac{\text{Net Weight of Study Drug}}{(1.12\text{g/day} * \text{Number of days in the study})} \right] * 100\%$$

xx.xx g

The number of days the subject administered study drug, the amount of product used, and the percent compliance will be summarized by treatment group and presented in a by-subject data listing. The subject listing will also include by-visit IP weights. Percent compliance will be calculated only for subjects who returned the study drug at the end of the treatment. In the listing, subjects who withdrew from the study early will be flagged.

7.5 Medical History

A by subject data listing of medical history will be presented. Medical history will be coded using MedDRA v20.0, and the number and percentage of patients experiencing at least 1 such diagnosis by MedDRA System Organ Class (SOC) and preferred term (PT) will be reported.

7.6 Concomitant Medication

Concomitant medications will be coded using the World Health Organization (WHO) dictionary. Results will be tabulated by anatomic therapeutic class (ATC) and preferred term.

This data will be summarized by treatment group. Previous and concomitant medications will be presented in a data listing.

7.7 Vital Signs and Physical Examination

Vital sign measurements will be presented for each subject in a data listing. Systolic blood pressure, diastolic blood pressure, heart rate, and weight will be summarized as actual value and change from baseline by visit.

All physical examination findings will be presented in a data listing.

7.8 Laboratory Data

Clinical laboratory values will be expressed in SI units reported by the central laboratory.

The actual value and change from screening will be summarized for each clinical chemistry, hematology, lipid panel, HbA1C and urinalysis parameters and by each visit. In the event of repeat values, the last non-missing value per visit will be used.

Sample for Serology was collected only at Baseline. Hence Serology data will be only provided in a listing.

All laboratory data will be also provided in data listings. Values outside of the lab parameter's normal range will be flagged as high, low, or abnormal based on the range of the test.

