10.2.8 Unscheduled Visit

If an event arises that requires subject to come in to the research center, subjects should be scheduled for the Unscheduled visit and assessments are performed based on investigator discretion.

Subjects will be encouraged to report any complications or adverse effects during their participation. Investigator may evaluate the subject at an unscheduled visit, if subject's condition will be considered as worsening.

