11.2.3 Laboratory Assessments

Blood samples will be taken at the times indicated in the [Schedule of Study Activities](#). Blood samples should be taken using standard venipuncture techniques. Blood sampling will be performed according to the site SOPs.

The following routine clinical chemistry, hematology and Lipid Panel will be performed according to the Schedule of Study Activities. Albumin, Alkaline Phos, ALT, AST, Total Bilirubin, BUN, BUN:Creatinine ratio, Calcium, Chloride, Creatinine, eGFR, Glucose, Potassium, Sodium, Uric Acid.

Lipid Panel: HDL Cholesterol, LDL cholesterol, Total Cholesterol, Triglycerides, VLDL Cholesterol, LDL/HDL Cholesterol Ratio, Non HDL Cholesterol.

Hematology: WBC, RBC, Hemoglobin, Hematocrit, Platelets, WBC Differential (Neutrophils, Lymphocytes, Monocytes, Eosinophils, Basophils), HbA1C.

Serology will only be done at Screening: HIV Ab, HCV Ab, HBsAg.

Urinalysis will be performed according to the Schedule of Study Activities.

Patients will be asked to fast for at least 8 hours before all blood tests are done.

The total blood volume collected for clinical labs for Screening visit will be approximately 20 ml of whole blood. Volume collected for subsequent visits would be approximately 10 ml of whole blood.

Any value outside the normal range will be flagged for the attention of the Investigator or designee at the site. The Investigator or designee will indicate whether or not the value is of clinical significance. If the result of the clinical chemistry test from the samples taken during the screening phase is indicated as clinically significant, the study subject will NOT be allowed into the study.

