6.7.3 Multiple Assessments

No multiple assessment for same visit are scheduled.

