7.9 Visit Windows

It is expected that all visits should occur according to the protocol schedule. All data will be tabulated per the evaluation visit as recorded on the CRF even if the assessment is outside of the visit window. In data listings, the relative day of all dates will be presented.

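### SAP 7.8 summarises the last repeat value at a visit; where an abnormal result prompted the repeat under the same visit label, the laboratory summaries understate abnormalities, and no worst-value or out-of-range summary offsets this

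*SAP*

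**What the plan says.** SAP v2.0 section 7.8 defines the laboratory summary: "The actual value and change from screening will be summarized for each clinical chemistry, hematology, lipid panel, HbA1C and urinalysis parameters and by each visit". For repeats it adds: "In the event of repeat values, the last non-missing value per visit will be used". SAP v1.0 has the same rule.

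Five other places bear on it.

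- SAP 6.7.3: "No multiple assessment for same visit are scheduled". Any repeat is therefore unplanned.
- Protocol 11.2.3: "Any value outside the normal range will be flagged for the attention of the Investigator or designee at the site". The investigator or designee then judges clinical significance. No retest is ordered.
- Protocol 10.2.8 allows unscheduled visits at which "assessments are performed based on investigator discretion".
- SAP 7.9: "All data will be tabulated per the evaluation visit as recorded on the CRF". Neither document says which visit label a retest receives.
- SAP 7.8 also keeps the raw data in view: "All laboratory data will be also provided in data listings", and values outside the "normal range will be flagged as high, low, or abnormal based on the range of the test".

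SAP 6.4 includes the SD, minimum and maximum among the statistics for continuous variables. The Appendix A table lists contain no laboratory table. Laboratory data appear in Appendix B as listings 16.2.4.1 to 16.2.4.3. No shift table, worst-value rule or by-arm count of out-of-range values is planned.

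**The concern.** A last-value rule is harmless when repeats occur for reasons unrelated to the result. It is selective when the result itself prompts the repeat. A value chosen because it was extreme contains, on average, some measurement or day-to-day error in that direction, so a second sample tends to fall back: high values fall and low values rise. The rule then puts the second value into the summary in place of the first.

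The values replaced in this way lie in the tails. The statistics most exposed are therefore the minimum, the maximum and the SD, which are where a reader of a descriptive safety table looks for a laboratory signal. SAP 8.2.1 names clinical chemistry and hematology among the safety variables under the primary safety endpoint. If one arm has more abnormal values, more of its values are open to replacement, and the contrast between arms shrinks.

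**Working it through.** The documents give no abnormality rate, retest rate or test-retest correlation, so there is no planned figure to reproduce. What follows is an illustration, and every numerical input is an assumption.

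**Inputs (assumed).** The analyte is standard normal in the vehicle arm. The upper limit is t = 1.96 (97.5th percentile). B244 shifts the analyte by d = 0.68 SD. First sample X and retest Y have correlation r. A share q of high first values is retested under the same visit label.

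**Step 1: how many high values stay high on retest.** P(Y > 1.96 | X > 1.96) is 0.249, 0.331 and 0.593 at r = 0.6, 0.7 and 0.9.

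**Step 2: effect on the mean.** If every high value is replaced (q = 1), an arm's mean falls by (1 − r) × φ(t − shift). At r = 0.7:
- B244: 0.3 × φ(1.28) = 0.3 × 0.1758 = 0.053 SD
- Vehicle: 0.3 × φ(1.96) = 0.3 × 0.0584 = 0.018 SD
- Loss in the difference: 0.053 − 0.018 = 0.035 SD, and 0.035 / 0.68 is about 5%

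The same formula gives a loss of 0.4 × (0.1758 − 0.0584) = 0.047 SD at r = 0.6 and 0.1 × 0.1174 = 0.012 SD at r = 0.9. Each loss is multiplied by q when only a share is retested.

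**Step 3: effect on the tail, r = 0.7.** The share above the limit is:

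| | B244 | Vehicle | Difference |
|---|---|---|---|
| First value | 10.0% | 2.5% | 7.5 points |
| Last value, q = 100% | 4.7% | 0.8% | 3.9 points |

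For other q the difference is 7.5 − q × (7.5 − 3.9):
- q = 50%: 7.5 − 1.8 = 5.7 points
- q = 25%: 7.5 − 0.9 = 6.6 points

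The SAP plans no such count. These percentages show only how strongly the rule acts on extremes.

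**Step 4: wider grid.** A simulation (2,000,000 draws per setting) retested values outside ±1.96 on both sides, with r = 0.5, 0.7 and 0.9 and q = 25%, 50% and 100%.
- With no true shift, the mean does not change, but the SD falls from 1.00 to between 0.91 and 0.99. The share out of range falls from 5.0% to between 0.9% and 4.5%.
- With a 1.0 SD shift, the mean falls from 1.00 to between 0.88 and 0.99 SD. The largest loss, 0.12 SD, is at r = 0.5 with every out-of-range value retested. The share above the limit falls from 16.9% to between 6.8% and 15.8%.

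At high r most of a sustained abnormality survives the retest. Noisy or transient abnormalities are largely removed.

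**Step 5: screening.** Section 7.8 measures change from screening, so the rule also applies to a repeated screening value and can alter the reference for change. Screening precedes randomization, so this adds no systematic difference between arms.

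**The case against.** The strongest objection is that the trigger is inferred. No passage orders a retest after an abnormal result, and a repeat may equally follow a lost or unusable sample, in which case taking the later value is right. This stands, and the point is conditional on it.

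Second, the mechanism needs the retest to carry the same visit label. Samples go to a central laboratory (Protocol 11.2.5), so an abnormal result may be known only after the subject has left. A retest entered as an unscheduled visit would replace nothing, because SAP 7.9 follows the CRF label. This also stands. It shows that the assignment of repeats to visits is itself a gap to close.

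Third, the data remain visible: all laboratory values are listed with flags, SAP section 7 separately requires abnormal values to be listed, and safety reporting is descriptive with no test. That limits the harm. A listing does not, however, give a comparison by arm.

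A reader might infer that the safety summaries as a whole are pulled toward normal. The documents do not support that. SAP 3.2.1 defines the safety endpoints as adverse events, and the synopsis bases the primary endpoint on AE and SAE numbers. Under Protocol 12.1.1 laboratory abnormalities become AEs through intervention or investigator judgement, independently of this rule.

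A reader might also take the fall from 7.5 to 3.9 points as the expected loss in a reported result. It is the extreme case in which every high value is retested, for an output the SAP does not plan.

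**Conclusion.** The concern holds in conditional form and is minor. When an abnormal first result prompts a repeat that is recorded under the same visit, SAP 7.8 puts a value that is on average more normal into the descriptive by-visit laboratory summaries. The minimum, maximum and SD are most affected, and no planned by-arm summary compensates.

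The effect on means is small: about 0.035 SD of a 0.68 SD shift at r = 0.7 with every high value retested, and no more than 0.12 SD anywhere on the grid examined. The actual size cannot be stated, because the share of abnormal values retested under the same label is unknown. It is zero if retests are always entered as unscheduled visits, or if repeats follow only unusable samples. The direction does not depend on the assumed values, provided the retest is imperfectly correlated with the first sample.

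**What to change.** Make three changes in SAP 7.8.

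1. Use the first valid scheduled value at each visit, including screening as the reference for change, for the actual-value and change summaries. Use a repeat only when the first sample is recorded as unusable.
2. State that any other retest, whether recorded under the same visit or an unscheduled one, does not replace the scheduled value.
3. Add a high/low count by arm based on each subject's worst post-baseline on-treatment value, including repeats and unscheduled results.

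The cost is a few SAP sentences, a programming rule and one added table. Unusable first samples must be flagged in the data so that the exception can be applied.

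While 7.8 is open, its use of change from screening should be reconciled with SAP section 7, which describes changes from baseline. That is a separate matter, but it decides which pre-treatment value the rule applies to.

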Statistical Analysis	
SAFETY ANALYSIS
 
The reporting of safety data is descriptive (arithmetic mean, standard deviation (SD), coefficient of variation (CV), median, minimum, and maximum) will be calculated for quantitative safety data as well as for the difference from baseline, when appropriate.
 
The analysis will include all subjects who receive at least one dose of investigational product. The variables for safety endpoints are AEs, Local Application Site Reactions, vital signs measurements, clinical chemistry and hematology. AEs will be summarized based on the frequency of AEs and their severity for all treated subjects. All AEs will be coded using Medical Dictionary for Regulatory Activities (MedDRA) and summarized by treatment group. Data will be summarized using preferred term and primary system organ class, including verbatim term, dose level, severity, and relationship to treatment, will be provided.

	
Concomitant medications will be listed by treatment and coded using the most recent version of the World Health Organization (WHO) Drug Dictionary (DD).
 
EFFICACY ANALYSIS
 
The Evaluable Period for the outcome variables will be weeks 1, 4, 8 and 12. The superiority of the drug over the vehicle will be tested at week 8 based on the probability of improvement from baseline with a continuity-corrected Z-tests comparing the change from baseline of treatments vs Placebo. For all other evaluable periods, descriptive statistics for the change from baseline will be shown.
 
The change from baseline score of Skindex-16 will be compared among treatments at Week 12 using an ANOVA.

--	---

Table of Contents

Contents

STATISTICAL ANALYSIS PLAN REVIEW AND APPROVAL	2
PROTOCOL SYNOPSIS	3
1 LIST OF ABBREVIATION	14
2 INTRODUCTION	16
2.1 Study Overview	16
2.2 Study Flowchart	18
2.3 Schedule of Activities	19
3 STUDY OBJECTIVE AND ENDPOINTS	21
3.1 Study Objectives	21
3.1.1 Primary Objective.....	21
3.1.2 Exploratory Objectives.....	21
3.2 Study Endpoints	21
3.2.1 Safety & Tolerability (Primary).....	21
3.2.2 Efficacy (Exploratory).....	21
4 STUDY DESIGN.....	22
4.1 Summary of Study Design.....	22
4.2 Definition of Study Drugs.....	22
4.3 Sample Size Considerations	23
4.4 Study Withdrawal	23
4.5 Early Discontinuation	24
5 PLANNED ANALYSIS.....	24
5.1 Final Analysis.....	24
6 GENERAL CONSIDERATION FOR DATA ANALYSIS AND HANDLING.....	24
6.1 General Summary Table and Individual Subject Data Listing	24

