[figure not shown]
Approximately 130 subjects are planned to be enrolled, and assuming a 20% drop out rate, the planned overall sample size for this clinical trial is approximately 104 adult male and female subjects, 18 years of age and older with mild to moderate rosacea. Subjects will be randomized at a 1:1 ratio (B244: Vehicle) at about 8 clinical research centers in the United States.

The entire study will consist of a total of 6 visits:

- Visit 1(Day -21 to -1): Screening will occur at Days -21 to -1, followed by Washout (Days -14 to -1).
- Visit 2(Baseline/ Day 1): Randomization will occur during the baseline visit for the study (Day 1).
- Visit 3 – 5(Day 7 \pm 2 [Week 1], Day 28 \pm 2 [Week 4], Day 56 \pm 2 [Week 8]): Clinical assessments of response to treatment will be made at Week 1(Day 7), Week 4 (Day 28), and Week 8 (Day 56).
- Visit 6(Day 84 \pm 2): Subjects will come back for a 4-week post-treatment follow up visit at Week 12 (Day 84).

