7 DATA ANALYSES

The data analysis will be conducted on all participant data when the trial ends. Subjects will be pooled across all sites. Data will be presented by treatment group and overall. Categorical variables will be summarized by frequency distributions (number and percentages of subjects) and continuous variables will be summarized by descriptive statistics (mean, standard deviation, etc.).

Adverse events will be summarized by treatment group using the Medical Dictionary for Regulatory Activities (MedDRA) system organ class and preferred term. Separate tabulations will be produced for all treatment-emergent AEs (TEAEs), treatment-related AEs (those considered by the Investigator as at least possibly drug related), SAEs, discontinuations due to AEs, and AEs Grade 3 severity. By-subject listings will be provided for any deaths, SAEs, and AEs leading to discontinuation.

Descriptive statistics for each treatment group will be provided for clinical laboratory values (e.g., hematology, serum chemistry, and urinalysis) and vital signs data, presented as both actual values and changes from baseline relative to each on-study evaluation. Abnormal clinical laboratory values will be listed.

All data will be provided in by-subject listings.

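### SAP 7.8 takes laboratory change from screening, against SAP section 7 and the protocol, and no planned output counts newly abnormal subjects per arm (minor)

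*SAP*

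**What the plan says.** **Reference for change.** SAP v2.0 section 7.8 states: "The actual value and change from screening will be summarized", for chemistry, hematology, lipids, HbA1C and urinalysis at each visit. Section 7 of the same SAP has laboratory and vital-sign data "presented as both actual values and changes from baseline relative to each on-study evaluation". Protocol section 14 has the same baseline rule.

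**Abnormal values.** SAP section 7 says: "Abnormal clinical laboratory values will be listed". Section 7.8 adds flags: "Values outside of the lab parameter's normal range will be flagged as high, low, or abnormal based on the range of the test".

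**Repeats.** Section 7.8: "In the event of repeat values, the last non-missing value per visit will be used".

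**Timing.** SAP 2.1: "Screening will occur at Days -21 to -1, followed by Washout (Days -14 to -1"). The SAP 2.3 schedule has chemistry, hematology and urinalysis at Screening, Baseline, Week 4, Week 8 and Early Termination.

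**Role of the data.** SAP 3.2.1 defines the safety endpoint by adverse events. SAP 8.2.1 also names chemistry and hematology as safety variables, reported descriptively in the Safety population.

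**The concern.** There are two separate problems in one short section.

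First, two rules in the same SAP point to different measurements. Two programmers working from it could produce different change tables and both be following the text. The rule in 7.8, which is the more specific one, is the one that departs from the protocol. It also folds into the on-study change whatever happened between screening and Day 1, including withdrawal of prohibited treatments.

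Second, a safety reader wants to know how many subjects in each arm were normal before dosing and abnormal afterwards. Means, medians and extremes by visit do not answer that, and a listing gives it only if someone tallies it. Safety is this trial's primary objective, so a short by-arm count for the named supporting variables would be expected in the report.

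**Working it through.** No figure in the plan is in dispute, so the check is mainly a reading of the texts against each other.

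**1. The two references.** For any post-dose result:

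(post-dose − screening) = (post-dose − Day 1) + (Day 1 − screening)

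The two versions agree only when the last term is zero. That term covers up to 21 days and, for subjects who need it, the washout. It therefore contains ordinary visit-to-visit variation plus any effect of stopping earlier treatment, and neither is caused by the study product. It arises before treatment starts, so it should not favour an arm on average; it affects the within-arm change and adds noise. SAP 6.6 does not settle the matter: it describes the Baseline visit but does not say which measured value is the reference, or what to use if the Day 1 value is missing.

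**2. What each planned output gives.**
- By-visit laboratory summaries (SAP 7 and 7.8): actual value and change by arm. Under SAP 6.4 continuous variables get n, mean, SD, median, minimum and maximum. A minimum or maximum can show that someone was out of range, but not how many subjects were.
- Flags and listings (SAP 7 and 7.8; Appendix B listings 16.2.4.1 to 16.2.4.3): individual results, with no totals.
- Adverse event tables (Appendix A, 14.3.x): a laboratory abnormality gets there only if it needs treatment or the investigator considers it an adverse event (protocol 12.1.1).
- Appendix A contains no laboratory table at all, not even for the summaries that 7.8 promises. Its silence on shifts therefore proves nothing by itself; the evidence is the listing rule in section 7. By contrast, physical examination does get normal/abnormal counts by arm (14.1.5.x).

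None of these gives subjects per arm moving from normal to abnormal.

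**3. The repeat rule.** Take a subject who is normal on Day 1, high at the Week 4 draw, and normal when that draw is repeated. The value used for Week 4 is the normal one, so the high result enters neither the Week 4 mean nor the Week 4 maximum. It stays in the listing. SAP 6.7.3 says no repeats are scheduled, so how often this would happen is unknown and no rate is claimed.

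**4. What a count would be worth.** Inputs: 130 enrolled and 104 completing, 1:1 (SAP 4.3), so 65 or 52 per arm.
- One subject is 1/65 = 1.5% or 1/52 = 1.9% of an arm.
- With no newly abnormal subject among n, the one-sided 95% upper limit solves (1 − p)^n = 0.05, so p = 1 − 0.05^(1/n). This gives 4.5% for n = 65 and 5.6% for n = 52.

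These describe the precision of the proposed count. They do not estimate harm from leaving it out.

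**The case against.** The strongest reply is that the listing rule is the protocol's own. Protocol section 14 also plans descriptive statistics by arm and a listing of abnormal values, and nothing in the documents requires a shift table. Abnormalities that matter most clinically should surface as adverse events. Analysis datasets are planned (SAP 6.3), so a count can be programmed whenever someone asks. SAP 6.4 and section 7 also promise counts and percentages for categorical variables, which would cover qualitative urinalysis by visit. The screening reference may be a drafting slip: 7.8 also places serology at Baseline, while protocol 11.2.3 places it at Screening. Since actual values are summarised at each visit, an approximate group change from Day 1 remains readable.

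Much of this stands, and it is why the point is minor. It does not remove the conflict between 7.8 and both section 7 and the protocol. By-visit frequencies would still not show movement from a normal reference to the worst later value.

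Some stronger readings are tempting but unsupported:
- *That the synopsis and the vital-signs section also contradict 7.8.* The synopsis wording, "will be calculated for quantitative safety data as well as for the difference from baseline, when appropriate", is qualified, and the rule in 7.7, "will be summarized as actual value and change from baseline by visit", concerns vital signs. The conflict is with section 7 and protocol section 14.
- *That the sites' clinical-significance calls are ready to tabulate.* Protocol 11.2.3 has the investigator make the call, but the documents do not show that it is an eCRF variable.
- *That nearly every post-dose clinically significant result must be new, because a significant screening chemistry result bars entry.* Blood is drawn again on Day 1, and no rule requires that result before dosing, unlike the pregnancy test (protocol 11.2.2). A significant value could first appear on Day 1 and persist.

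**Conclusion.** The point holds as a minor correction and reporting improvement. The reference in SAP 7.8 conflicts with SAP section 7 and protocol section 14; that follows from the text and needs no assumption. The absence of a by-arm count of newly abnormal subjects follows from the listing rule and from what the planned summaries contain.

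The size is limited. A reader might infer that the primary safety analysis is compromised. It is not: that endpoint is built on adverse events, no planned analysis is invalidated, and the values remain in listings sorted by treatment group (SAP 6.1). What is lost is a clear within-subject reference and a direct count for supporting variables, where one subject is 1.5% to 1.9% of an arm. The documents give no basis for saying how many subjects would be affected by the reference choice or by the repeat rule.

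**What to change.** Before database lock:

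1. In SAP 7.8, replace the screening reference with the last pre-dose value (Day 1, or Screening if Day 1 is missing), and use it for all laboratory change summaries.
2. Add to 7.8 and Appendix A 10.1.3 one descriptive Safety-population table by arm, without p-values. For each parameter, show the shift from the reference category (low/normal/high, or normal/abnormal) to the worst post-baseline category. Include repeat, unscheduled and Early Termination values, and give separate worst-low and worst-high columns where a parameter can move both ways. Keep the last-repeat rule for the by-visit summaries only.
3. Add n (%) of subjects with a new clinically significant value only if that call is captured in the database.

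The first change costs one sentence. The table costs programming and review, and it is long because many parameters are covered. Some subjects in both arms will cross a range limit by chance, which is a reason to keep it descriptive. No extra visits, samples or subjects are needed.
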